- **Best response according to tumor marker evaluation (CA-125)** will be the best response obtained according to GCIG criteria. Irrespectively of treatment arm, tumor marker assessment will be performed symmetrically at baseline and every eight weeks from randomization until evidence of PD.
- **Treatment safety profile:** AEs, serious adverse events (SAEs) and laboratory abnormalities will be coded by the Medical Dictionary for Regulatory Activities (MedDRA), graded according to the NCI-CTCAE v. 4 and analyzed. Dose reductions or delays required due to treatment-related AEs, and reasons for treatment discontinuations will be also assessed.
- **Patient-reported outcomes (PRO):** To measure the quality of life of patients, EORTC QLQ-C30 and EORTC QLQ-OV28 questionnaires will be completed by the patients every eight weeks in all three treatment arms.

- **Plasma pharmacokinetics (PK) of PM01183** will be evaluated using a sparse sampling scheme in the PM01183 treatment arm (Arm A). Details will be given in a population PK analysis plan and the results of the population PK analysis will be presented in a separate report.
- **Subgroup analyses:** Subgroup analyses of the PM01183 arm *vs.* PLD or topotecan outcomes will be performed.
- **Pharmacogenetics:** This analysis will be performed in those patients who signed the IC for the PGx sub-study. The presence or absence of known polymorphisms from a single sample collected just before the PM01183 treatment start will be assessed to explain the individual variability in the main PK parameters.
- **Pharmacogenomics:** This exploratory analysis will be performed in those patients treated in any arm who signed the IC for the PGx sub-study. Samples from Arm B will be used as controls in order to differentiate between the prognostic or predictive value of any obtained finding. mRNA or protein expression levels of factors involved in DNA repair mechanisms, or related to the mechanism of action of PM01183 or to the pathogenesis of the disease, will be evaluated from prior available tumor tissue samples obtained at diagnosis or relapse. Their mutational status might also be analyzed. Their correlation with the clinical response and outcome after treatment will be assessed.

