7 STATISTICAL METHODOLOGY FOR SAFETY

7.1 *Toxicity and Adverse Events*

Patients will be evaluable for safety if they have received any partial or complete treatment infusion. All AEs will be graded according to the NCI-CTCAE v.4. Treatment delays, dose reduction requirements and reason for treatment discontinuation will be monitored throughout the study.

The safety profile of patients will be monitored throughout the treatment and up to 30 days after the last treatment infusion (end of treatment, EOT), or until the patient starts a new antitumor therapy or until the date of death, whichever occurs first.

Any AEs will be coded using to the Medical Dictionary for Regulatory Activities (MedDRA). Treatment-related AEs will be followed, whenever possible, until recovery to at least grade 1 or stabilization of symptoms, whenever possible.

Summary of overall AEs will be done by body system and preferred term, by severity (worst toxicity grade) and by relationship. Tables will be sorted by body system/preferred term.

A frequency table will be made for the AEs leading to cycle delay, dose reduction, skipped dose (topotecan only), or withdrawal of study medication. AEs leading to permanent treatment stop and AEs with outcome of death will also be presented by relationship to drug.

Exploratory Fisher's exact tests will be performed to compare the incidence of grade 4 or grade 3/4 AEs between treatment arms.

7.2 *Clinical Laboratory Evaluation*

Laboratory results will be classified according to the NCI-CTCAE v.4.

The worst grade per patient will be tabulated during overall treatment and per cycle for hematology values [white blood cells (WBC), absolute neutrophil count (ANC), lymphocyte count, platelet count and hemoglobin] and for the following biochemistry tests: alanine aminotransferase (ALT), aspartate aminotransferase (AST), total bilirubin, alkaline phosphatase (AP), creatine phosphokinase (CPK), creatinine, glucose, sodium, potassium and albumin.

Exploratory Fisher's exact tests will be performed to compare the incidence of grade 4 or grade 3/4 laboratory evaluations between treatment arms.

7.3 *Physical Examination Findings*

Tables summarizing the performance status (PS), height, body weight and BSA (according to the Dubois and Dubois formula) at baseline will be prepared.

In addition, changes in the ECOG PS and body weight of each patient during the treatment compared to baseline will be presented.

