8.4 Patient-reported Outcomes (PRO)

To measure the quality of life of patients, EORTC QLQ-C30 and EORTC QLQ-OV28 questionnaires will be analyzed every eight weeks from randomization and while on treatment.

PRO will be analyzed by means of longitudinal modelling and T-test comparisons to determine if efficacy and side effects are accompanied by measurable changes. The analysis will be performed on summary scores of EORTC QLQ-C30 and EORTC QLQ-OV28 questionnaires, as well as on subscales and individual symptoms.

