12.8 PRO at treatment

Completion rate is defined as the number of patients with answer to item X in the numerator and the number of patients on treatment in each time point as denominator.

Missing data will not be taken into account in the analyses; anyway, if the quantity is considered relevant then supportive analyses will be performed applying a conservative approach of assuming missing data as failures.

Table 12.8.1 Completion rate

Item	Cycle	PM01183		Control	
		Missing (%)	Completed (%)	Missing (%)	Completed (%)
EORTC QLQ-C30					
Item 1	Baseline				
	Week 6				
	...				
....	Baseline				
	...				
Any item	Baseline				
	Week 6				
	...				
EORTC QLQ-OV28					
Item 31	Baseline				
	Week 6				
	...				
....	Baseline				
	...				
Any item	Baseline				
	Week 6				
	...				
EORTC QLQ-C30 and QLQ-OV28					
Any item	Baseline				
	...				

Table 12.8.2 T-test change vs. baseline

Item	Cycle	PM01183		Control*		p-value
		N	Mean (std)	N	Mean (std)	
*Control refers to PLD and/or topotecan						
Item 1	Week 6					
	Week 12					
	...					
....	Week 6					
	Week 12					
	...					
Item 58	Week 6					
	Week 12					
	...					
*Control refers to PLD						
Item 1	Week 6					
	Week 12					
	...					
....	Week 6					
	Week 12					
	...					
Item 58	Week 6					
	Week 12					
	...					
*Control refers to topotecan						
Item 1	Week 6					
	Week 12					
	...					
....	Week 6					
	Week 12					
	...					
Item 58	Week 6					
	Week 12					
	...					

Table 12.8.3 Percentage of patients with an improvement $\geq 10\%$ vs. baseline

Item	Cycle	PM01183		Control*		p-value
		N	%	N	%	
*Control refers to PLD and/or topotecan						
Item 1	Week 6					
	Week 12					
	...					
....	Week 6					
	Week 12					
	...					

[figure not shown]
Item	Cycle	PM01183		Control*		p-value
		N	%	N	%	
Item 58	Week 6					
	Week 12					
	...					
*Control refers to PLD						
Item 1	Week 6					
	Week 12					
	...					
....	Week 6					
	Week 12					
	...					
Item 58	Week 6					
	Week 12					
	...					
*Control refers to topotecan						
Item 1	Week 6					
	Week 12					
	...					
....	Week 6					
	Week 12					
	...					
Item 58	Week 6					
	Week 12					
	...					

Longitudinal analyses will be performed assuming a mixed-effect model with treatment (Y), time effect (days after baseline), and a time-treatment interaction as covariates, using a covariance structure of autoregressive order 1.

Table 12.8.4 Mixed effect model

Item	Estimated point change per day	p-value	Mean change during treatment

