*Control refers to PLD and/or topotecan			
Item 1			
....			
Item 58			
*Control refers to PLD			
Item 1			
....			
Item 58			
*Control refers to topotecan			
Item 1			
....			
Item 58			

Figures 12.8.5-12.8.62 Means plot by each item

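### The PRO secondary endpoint is tested item by item on 58 items, with no lead comparison, significance level or exploratory label

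*SAP*

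**What the plan says.** PRO is a secondary objective (SAP 4.2) and is listed among the secondary endpoints (SAP 4.3), where the "questionnaires will be completed by the patients every eight weeks in all three treatment arms". Under SAP 8.4, "PRO will be analyzed by means of longitudinal modelling and T-test comparisons to determine if efficacy and side effects are accompanied by measurable changes". The outcomes are listed without ranking: "The analysis will be performed on summary scores of EORTC QLQ-C30 and EORTC QLQ-OV28 questionnaires, as well as on subscales and individual symptoms". Protocol 8.2.3 is equally general, and Protocol 8.2 leaves specifics to the SAP.

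SAP 12.8 provides the table shells:

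- "Table 12.8.2 T-test change vs. baseline" has rows for Items 1 to 58 at Week 6, Week 12 and onward, with N, mean and SD for each arm and one p-value per row.
- Table 12.8.3 has the same layout for the percentage of patients improved by at least 10% from baseline.
- Table 12.8.4 has a mixed-model p-value for each item, from one fit over time rather than by week.

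Each table is repeated for three comparators. In the first block, "Control refers to PLD and/or topotecan"; the second is PLD alone and the third topotecan alone. Figures 12.8.5 to 12.8.62 ("Means plot by each item") number 58, which confirms the item count.

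Elsewhere the SAP does label tests. In SAP 7.1, "Exploratory Fisher's exact tests will be performed to compare the incidence of grade 4 or grade 3/4 AEs between treatment arms". SAP 8.9 calls the efficacy subgroup comparisons with PLD or topotecan preplanned exploratory analyses. SAP 6.1 controls type I error if OS is analysed more than once. Nothing comparable is said about PRO.

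**The concern.** A secondary endpoint whose tests are meant to determine something needs a stated test that does so. Here the reader is given several hundred p-values and no rule for weighing them. The methods can also disagree on the same item, and the SAP does not say which would count.

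The trial is open-label. Protocol 1.1 places quality of life and symptom control among the main aims of treating recurrent disease, so a quality-of-life or symptom difference would attract attention. If the shells are filled in as drawn, some nominally significant single-item differences are probable even when the arms do not differ. The plan offers no basis for telling these from real ones, in either direction.

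**Working it through.** **Plan's own figure.** The documents give no error rate, power or test count for PRO. The only design level is the one-sided 2.5% in SAP 5.2, which belongs to PFS by IRC. That design reproduces: 4 x (1.960 + 1.282)² / (ln 0.7)² = 330.4, so 331 events against the stated 332. It sets no level for PRO.

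**Inputs from the documents.** 58 items; two printed post-baseline weeks (the shells continue beyond them); three comparators; two by-week tables; one mixed model per item and comparator.

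**Assumed inputs.** Two-sided 5% for each PRO test, as no level is stated; each test holds its nominal level; a common inter-item correlation of 0.3 to 0.8.

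**Step 1: count the p-values.**

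| Set | Arithmetic | p-values | Expected false positives at 5% |
|---|---|---|---|
| Pooled control, Tables 12.8.2 and 12.8.3 | 58 x 2 weeks x 2 tables | 232 | 11.6 |
| The same plus Table 12.8.4 | 232 + 58 | 290 | 14.5 |
| All three comparators, all three tables | 290 x 3 | 870 | 43.5 |

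The expected number is the count times 0.05, whatever the correlation between tests. At 2.5% it halves: 232 x 0.025 = 5.8.

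The first row is the firm one. Tables 12.8.2 and 12.8.3 show both arms and one p-value per row, so they read as between-arm tests. Table 12.8.4 has no arm columns and does not say whether its p-value tests the time slope, the treatment term or their interaction. A slope test is not a null test merely because the arms are identical. The SAP also does not name the test behind Table 12.8.3; an exact test would run somewhat below 5%, making 11.6 slightly high. The t-tests alone give 58 x 2 = 116 p-values, or 5.8 expected.

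**Step 2: chance of at least one false positive in the smallest slice** (58 items, one week, pooled control, t-test only).

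If the items were independent: 1 - 0.95^58 = 94.9%. They are not, so write each item's test statistic under the null as √ρ F + √(1-ρ) eⱼ, with F and the eⱼ independent standard normals, and find the chance that any of the 58 exceeds 1.96 in absolute value:

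| ρ | At least one p < 0.05 | At least one falsely favouring PM01183 |
|---|---|---|
| 0.3 | 84% | 47% |
| 0.5 | 66% | 33% |
| 0.8 | 31% | 16% |

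Numerical integration and a simulation of 200,000 replicates agree. A separate simulation with patient-level t-tests (150 per arm assumed) gave 66% at ρ = 0.5.

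**Step 3: add the second printed week.** With an assumed within-item correlation of 0.6 between weeks, still t-tests against pooled control, the chance becomes 96%, 86% and 48% at ρ = 0.3, 0.5 and 0.8.

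These counts cover single items only. SAP 8.4 also promises summary scores and subscales, which the shells do not show.

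**The case against.** **No decision rule exists to be abused.** A reader might infer that the PRO conclusion will rest on whichever item reaches significance. The documents do not say so. They state no PRO decision rule and announce no PRO claim. PRO is absent from the main summary of efficacy analyses at the end of SAP 6.2, and its on-treatment tables sit in the safety part of Appendix I. This objection stands: what can be shown is a missing rule, not a planned misuse. But placement is not a label, and SAP 7.1 shows that safety tests are called exploratory when that is meant.

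**The largest count overstates the problem.** A reader might take 870 tests and 43.5 false positives as the headline. Two thirds of that count (580) are PLD-only and topotecan-only blocks. SAP 8.9 arguably makes these exploratory, although it speaks of efficacy subgroups and does not mention PRO. The Table 12.8.4 p-values may not be between-arm tests at all. So 870 is an upper count and 232 the firm one.

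**PRO is not alone.** PFS by IA, response rate, duration of response and CA-125 response also print p-values without a hierarchy or a label. That is correct, and PRO should not be presented as a unique lapse. What differs is scale: 58 outcomes, repeated by week, with none ranked first.

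**Correlation softens the rates.** At ρ = 0.8 the one-week slice is 31% and the two-week figure 48%, both below even odds. A false positive is therefore not certain in every slice. Even 31% is about six times 5%.

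**Conclusion.** The point holds as an omission in the SAP. As the shells are drawn, pooled control alone yields 232 between-arm p-values and about 11.6 expected false positives, or 290 and 14.5 if the mixed-model p-value is also a between-arm test. The smallest slice carries about a 66% chance of at least one false positive, with a range of 31% to 84%. These figures rest on an assumed two-sided 5% level and on assumed correlations that the documents do not supply; the item, table and week counts come from the SAP.

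The documents do not support going further and saying that a chance-driven quality-of-life conclusion is built into the plan. The primary PFS test and its error rate, data collection and patient safety are untouched. The matter should be settled before the PRO data are analysed, but it does not threaten the trial's main result.

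**What to change.** In SAP 8.4, name one lead PRO comparison. A workable choice is QLQ-C30 global health status/QoL, PM01183 against pooled control, using the mixed model that SAP 12.8 already specifies (treatment, time and their interaction, first-order autoregressive covariance). State which between-arm term is tested, at two-sided 5%, and report it with a 95% confidence interval. Global QoL is a suggestion: the SAP already uses its baseline value as a covariate in 6.2 but nowhere designates it as the lead. Using the mixed model keeps the longitudinal approach that SAP 8.4 lists first and avoids picking a single week.

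State that all other items, scales, weeks and methods, and the PLD-only and topotecan-only comparisons, are exploratory. Report them as estimates with confidence intervals, and base no claim on them. In Table 12.8.4, add arm columns and name the tested term. While the shells are open, reconcile their Week 6 and Week 12 rows with the eight-weekly questionnaire schedule.

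One prespecified comparison restores a 5% false-positive rate for the lead PRO question. The cost is SAP text and table-shell edits, with no new data or patients. The sponsor gives up claims resting on a single item or a single control drug.

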8.5 Subsequent Therapies

A table summarizing the subsequent therapies received after discontinuation will be shown. Special attention will be focused on patients receiving any platinum compound as first subsequent treatment, and analyses to test between treatment arms if potential platinum-free interval prolongation is associated with survival.

8.6 Imputation in Incomplete Dates

Dates of certain historical or current clinical activities are key component for statistical analysis. An incomplete date results from a missing day, month or year; in that case, the missing figure can be imputed allowing for the calculation of variables, such duration and time to certain event. However, when all of them, day, month and year, are missing no imputation will be done.

Before randomization

All variables needed to summarize for example prior information (e.g. first diagnosis date) where partial information is available will be subject of imputation by means of SAS programming. If the day of a date is unknown then the imputed day will be 1, if the month is also unknown then the imputed date will 1/July. This assumption will be valid if the imputed date is earlier than the randomization date; otherwise, the imputed date will be the first day of the randomization month date (i.e. 01/Randomization month date/year).

Between treatment start and end of treatment

All date variables during treatment where information is needed and is not fully available, for example adverse events or concomitant medications, will be subject of imputation by means of SAS programming. If the day of a date is unknown then the imputed day will be 1, if the month and/or year is also unknown then the imputed date will 1/January (this assumption will be valid if the imputed date is earlier than the treatment start date; otherwise, the imputed date will be the treatment start date).

After end of treatment

A conservative approach for the variables collecting information after end of treatment where partial information is available (e.g., main time-to-event variables; PFS and OS) will be imputed by means of SAS programming. The following rules will be implemented: if the day of a date is unknown then the imputed day will be 1; if the month is also unknown, then the imputed date will be 1/July. This assumption will be valid if the imputed date occurs later than the last drug administration date; otherwise, the imputed date will be the last drug administration date plus 1 day.

If the date of subsequent therapy is incomplete (day or month is missing) and the patient had documented disease progression, the date of subsequent therapy will be imputed to the end of the month when the progression occurred. If the subsequent therapy is given before progression to the study treatment, the rules specified above will apply.

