11.1.4 Signs and Symptoms at Baseline

Signs and symptoms refer to any AE with onset date before the first treatment dose.

Table 11.1.4.1 Patients with signs and symptoms at baseline

No. of signs and symptoms per patient	PM01183		Control					
			Total		PLD		Topotecan	
	N	%	N	%	N	%	N	%
0								
1								
2								
≥ 3								
Median (range)								
Mean (std)								

Table 11.1.4.2 Signs and symptoms at baseline (MedDRA coded)

SOC	Preferred term	Total	Grade 1		Grade 2		Grade 3		Grade 4		Grade 1-4	
			N	N	%	N	%	N	%	N	%	N
PM01183												
Gastrointestinal disorders	Constipation											
	Diarrhoea NOS											
	...											
Control												
Gastrointestinal disorders	Constipation											
	Diarrhoea NOS											
	...											

Listing 11.1.4.3 Signs and symptoms at baseline

Treatment arm*	Patient id.	Sign/symptom	Grade	Onset date

*PM01183/PLD/Topotecan

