12.2 Adverse Events (AEs)

12.2.1 Adverse Events

Treatment emergent AEs will be described irrespective of their relationship to the drug and as drug-related events stated as Related to Study Drug or Unknown. Safety will be described according to the NCI-CTCAE v4. AEs consisting of laboratory abnormalities (e.g., neutropenia) may be under-reported as AEs. Since these events are better evaluated using objective laboratory results, laboratory abnormalities will be discussed in Section 12.4.

The type of toxicity and worst grade or severity by cycle and by patient will be summarized according to System Organ Class (SOC) and Preferred Term (PT) as per the MedDRA dictionary. Subsequent grouping of similar or clinically related items might be appropriate at the time of the analysis. Tables will be organized by category of events using SOC and in descending frequencies (e.g. higher to lower).

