12.5 Subgroup Analyses Related to Safety

Information for laboratory abnormalities comes from hematology/biochemistry forms and not from AE form.

Table 12.5.1 Worst grade 3/4 by patient in special subgroups (Age)

Laboratory abnormalities/ drug-related AEs	<65 years-old			≥65 years-old		
	No. of patients evaluated	Grade 3/4	%	No. of patients evaluated	Grade 3/4	%
PM01183						
Thrombocytopenia						
Neutropenia						
ALKP						
Bilirubin						
SGOT-AST						
SGPT-ALT						
CPK						
Nausea						
Vomiting						
Fatigue						
Other*						
Control						
Thrombocytopenia						
Neutropenia						
ALKP						
Bilirubin						
SGOT-AST						
SGPT-ALT						
CPK						
Nausea						
Vomiting						
Fatigue						
Other*						

*Any drug-related toxicity present in >=5% of patients in any group.

Table 12.5.2 Worst grade 3/4 by cycle in special subgroups (Age)

Laboratory abnormalities/ drug-related AEs	<65 years-old			≥65 years-old		
	No. of cycles evaluated	Grade 3/4	%	No. of cycles evaluated	Grade 3/4	%
PM01183						
Thrombocytopenia						
Neutropenia						
ALKP						
Bilirubin						
SGOT-AST						
SGPT-ALT						
CPK						
Nausea						
Vomiting						
Fatigue						
Other*						
Control						
Thrombocytopenia						
Neutropenia						
ALKP						
Bilirubin						
SGOT-AST						
SGPT-ALT						
CPK						
Nausea						
Vomiting						
Fatigue						
Other*						

*Any drug-related toxicity present in $\geq 3\%$ of cycles in any group.

Table 12.5.3 Worst grade 3/4 by patient in special subgroups (Race)

Laboratory abnormalities/ drug-related AEs	White			Other		
	No. of patients evaluated	Grade 3/4	%	No. of patients evaluated	Grade 3/4	%
PM01183						
Thrombocytopenia						
Neutropenia						
ALKP						
Bilirubin						
SGOT-AST						
SGPT-ALT						
CPK						
Nausea						
Vomiting						
Fatigue						
Other*						
Control						
Thrombocytopenia						
Neutropenia						
ALKP						
Bilirubin						
SGOT-AST						
SGPT-ALT						
CPK						
Nausea						
Vomiting						
Fatigue						
Other*						

*Any drug-related toxicity present in $\geq 5\%$ of patients in any group.

Table 12.5.4 Worst grade 3/4 by cycle in special subgroups (Race)

Laboratory abnormalities/ drug-related AEs	White			Other		
	No. of cycles evaluated	Grade 3/4	%	No. of cycles evaluated	Grade 3/4	%
PM01183						
Thrombocytopenia						
Neutropenia						
ALKP						
Bilirubin						
SGOT-AST						
SGPT-ALT						
CPK						
Nausea						
Vomiting						
Fatigue						
Other*						
Control						
Thrombocytopenia						

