A conservative approach for the variables collecting information after end of treatment where partial information is available (e.g., main time-to-event variables; PFS and OS) will be imputed by means of SAS programming. The following rules will be implemented: if the day of a date is unknown then the imputed day will be 1; if the month is also unknown, then the imputed date will be 1/July. This assumption will be valid if the imputed date occurs later than the last drug administration date; otherwise, the imputed date will be the last drug administration date plus 1 day.

Changes to (Section 8.6 Imputation in Incomplete Dates):

Dates of certain historical or current clinical activities...

Before randomization

All variables needed to summarize...

Between treatment start and end of treatment

All date variables during treatment where information is needed and is not fully available, for example adverse events or concomitant medications, will be subject of imputation by means of SAS programming. If the day of a date is unknown then the imputed day will be 1, if the month and/or year is also unknown then the imputed date will 1/January (this assumption will be valid if the imputed date is earlier than the treatment start date; otherwise, the imputed date will be the treatment start date).

After end of treatment.

A conservative approach for the variables collecting information after end of treatment where partial information is available (e.g., main time-to-event variables; PFS and OS) will be imputed by means of SAS programming. The following rules will be implemented: if the day of a date is unknown then the imputed day will be 1; if the month is also unknown, then the imputed date will be 1/July. This assumption will be valid if the imputed date occurs later than the last drug administration date; otherwise, the imputed date will be the last drug administration date plus 1 day.

If the date of subsequent therapy is incomplete (day or month is missing) and the

patient had documented disease progression, the date of subsequent therapy will be imputed to the end of the month when the progression occurred. If the subsequent therapy is given before progression to the study treatment, the rules specified above will apply.

Table/listing added (Section 10.1 Patient Disposition):

Listing 10.1.8 Patients assigned to incorrect strata at the time of randomization

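### The SAP's on-treatment date-imputation rule is inverted: it keeps impossible pre-dose dates, overwrites plausible ones, and can turn early adverse events into baseline symptoms

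*SAP*

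**What the plan says.** SAP 8.6 has three rules, one for each period.

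- **Before randomization.** The imputed date stands if it is earlier than the randomization date.
- **Between treatment start and end of treatment.** The scope is "All date variables during treatment where information is needed and is not fully available, for example adverse events or concomitant medications". The rule begins "If the day of a date is unknown then the imputed day will be 1, if the month and/or year is also unknown", in which case 1 January is used. A parenthesis then makes the result "valid if the imputed date is earlier than the treatment start date; otherwise, the imputed date will be the treatment start date".
- **Once treatment has ended.** "This assumption will be valid if the imputed date occurs later than the last drug administration date"; otherwise the date becomes the day after last drug administration.

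The History of Changes (SAP section 15) lists the on-treatment paragraph as newly added, so it is current text. Nothing elsewhere corrects it.

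Two safety sections depend on onset dates. SAP 11.1.4 states: "Signs and symptoms refer to any AE with onset date before the first treatment dose". SAP 12.2.1 states: "Treatment emergent AEs will be described irrespective of their relationship to the drug". Neither says how a partial onset date is to be treated, and 12.2.1 does not define treatment-emergent.

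**The concern.** The first and third rules point the right way: a pre-randomization date should fall before its anchor, and a post-treatment date after its anchor. The on-treatment period follows its anchor, but its rule carries the wording of the pre-randomization rule. It therefore accepts exactly the dates that are impossible for an on-treatment event and discards the possible ones.

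At stake is the split between baseline symptoms and treatment-emergent events. Early on-treatment events moved to baseline drop out of the toxicity summaries. They can also raise the baseline grades in the signs-and-symptoms shift table (SAP 12.2.3). Concomitant-medication timing is exposed in the same way, as is the cycle assigned to an adverse event if that is derived from dates, which the SAP does not say.

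The scope is limited. For the safety subgroup tables, SAP 12.5 says "Information for laboratory abnormalities comes from hematology/biochemistry forms and not from AE form", and 12.2.1 likewise refers laboratory abnormalities to the laboratory results. Cycle delays and dose reductions use drug-administration CRF items (SAP 8.3). The primary test does not use this rule.

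**Working it through.** The plan gives no figure on this point, so the check applies the rule as written and then with the condition reversed.

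**Formula.** Let *s* be the first-dose date and *i* the imputed date: the 1st of the stated month, or 1 January of the stated year if the month is missing.

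- As written: *i* if *i* < *s*, otherwise *s*. The result is min(*i*, *s*), never later than Day 1.
- Reversed: *i* if *i* ≥ *s*, otherwise *s*. The result is max(*i*, *s*), never before Day 1.

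**Two readings.** The parenthesis may govern both the missing-day and the missing-month clause (reading A), or only the missing-month clause (reading B). Under B, missing-day dates have no floor at all.

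**Worked dates, first dose 16 March 2015.**

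| Recorded onset | Reading A | Reading B | Reversed |
|---|---|---|---|
| March 2015 | 1 Mar 2015 | 1 Mar 2015 | 16 Mar 2015 |
| May 2015 | 16 Mar 2015 | 1 May 2015 | 1 May 2015 |
| 2015 | 1 Jan 2015 | 1 Jan 2015 | 16 Mar 2015 |
| 2016 | 16 Mar 2015 | 16 Mar 2015 | 1 Jan 2016 |

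The first row is wrong under both readings. The displacement can be large under A: with first dose on 15 January 2015, an event dated June 2015 moves to 15 January, 137 days before 1 June.

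**Share misplaced among partial dates.** Assumptions: first-dose dates uniform over 1 January 2015 to 30 June 2016 (547 days, matching the planned 18-month enrolment), and true onset uniform over the stated window.

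An event dated only to the first-dose month falls before first dose for 529 of 547 start dates (529/547 = 96.7%) under either reading. The other 18 are starts on the 1st of a month, where the imputed date equals Day 1.

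| Missing part, onset window | Rule | Before first dose | Day 1 | Later |
|---|---|---|---|---|
| Day, 21 days | A | 63.8% | 36.2% | 0% |
| | B | 63.8% | 3.3% | 32.9% |
| | Reversed | 0% | 67.1% | 32.9% |
| Day, 84 days | A | 17.5% | 82.5% | 0% |
| | B | 17.5% | 1.2% | 81.3% |
| | Reversed | 0% | 18.7% | 81.3% |
| Month, 84 days | A or B | 92.0% | 8.0% | 0% |

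For a 28-day first cycle with the day missing, 52.3% fall before first dose under either reading.

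**Sensitivity.** The missing-day shares barely move with the enrolment start, but the pre-dose share falls to about 9% for a 168-day window. The missing-month share is 84.7% if enrolment starts on 1 July 2015 (84 days). For 168 days it is 84.4% with a January start and 69.5% with a July start.

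**Secondary point: after end of treatment.** This rule has the right direction, but its only floor is last drug administration. Take a last infusion on 10 March and a patient documented alive on 20 October. A death dated October is imputed to 1 October, 19 days before she was known to be alive. A death dated to that year only is imputed to 1 July, 111 days before.

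**The case against.** The best counter-argument concerns weight rather than correctness. No confirmatory analysis uses the rule, the same rule applies in both arms, and the safety comparisons are exploratory Fisher tests. The neighbouring rules make the copying slip obvious, so a programmer may well correct it. The events that matter most are least likely to have partial dates: serious events and all febrile neutropenia must be reported within 24 hours (protocol 7.4.1 and 7.4.2), and monitors check CRF and SAE data against source (protocol 7.5). All of this stands. It limits the likely size but does not make the rule right. A programmer who follows the text produces wrong output, and one who silently corrects it departs from the SAP.

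A second objection is that a record must already be regarded as on-treatment before this rule is chosen, so the imputed date need not reclassify it. That is fair in part. The move to baseline rests on the onset-date definition in 11.1.4, which does not say whether imputed dates count. But nothing in the SAP prevents that use.

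A third is that the rows of Table 12.2.2.1 for delays and reductions associated with adverse events appear to draw on adverse-event records, so they may also be touched. That would widen the scope a little.

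Finally, the death-date point concerns a different rule and is an edge case. It is kept only as a secondary remark.

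**Conclusion.** The concern holds. The on-treatment rule is wrong as written, and the wording alone shows it. Where the condition applies, no date after Day 1 can result. Under either reading, an event dated only to the first-dose month is imputed before first dose unless dosing began on the 1st.

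The absolute effect cannot be stated because the number of partial dates is unknown. The shares are conditional on a date being partial and on the uniform-onset and enrolment assumptions; the missing-month share also depends on the assumed calendar start. The finding that none fall before first dose once the condition is reversed does not depend on those assumptions. This should be corrected before the safety tables are programmed, but it does not threaten the primary result.

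**What to change.** Rewrite the on-treatment paragraph of SAP 8.6:

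1. For adverse-event onset and medication start dates whose known month and year are compatible with on-treatment onset, keep the imputed date if it is on or after treatment start; otherwise use treatment start. State that this covers both missing-day and missing-month dates.
2. Leave dates whose known month and year lie wholly before first dose as pre-treatment.
3. Do not set a partial end date earlier than the record's own start date.
4. Say what is done when the year is missing. The present text sends such dates to 1 January without saying of which year.
5. State in 11.1.4 and 12.2.1 whether imputed onset dates decide between baseline and treatment-emergent.

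For the secondary point, impute a partial death date no earlier than the day after the last documented date alive, and a partial progression date no earlier than the day after the last progression-free tumor assessment. A survival telephone contact is not such an assessment.

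The cost is a few SAP sentences and a small programming change, with no new data.
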